16.2.3. Informed Consent

Each subject (or a legally acceptable representative) must give written consent according to local requirements after the nature of the study has been fully explained. The ICF(s) must be signed before performance of any study-related activity. The ICF(s) that is/are used must be approved by both the sponsor and by the reviewing IEC/IRB and be in a language that the subject can read and understand. The informed consent should be in accordance with principles that originated in the Declaration of Helsinki, current ICH and GCP guidelines, applicable regulatory requirements, and sponsor policy.

Before enrollment in the study, the investigator or an authorized member of the study-site personnel must explain to potential subjects or their legally acceptable representatives the aims, methods, reasonably anticipated benefits, and potential hazards of the study, and any discomfort participation in the study may entail. Subjects will be informed that their participation is voluntary and that they may withdraw consent to participate at any time. They will be informed that choosing not to participate will not affect the care the subject will receive for the treatment of his or her disease. Subjects will be told that alternative treatments are available if they refuse to take part and that such refusal will not prejudice future treatment. Finally, they will be told that the investigator will maintain a subject identification register for the purposes of long-term follow-up if needed and that their records may be accessed by health authorities and authorized sponsor personnel without violating the confidentiality of the subject, to the extent permitted by the applicable law(s) or regulations. By signing the ICF the subject or legally acceptable representative is authorizing such access, which includes permission to obtain information about his or her survival status. It also denotes that the subject agrees to allow his or her study physician to recontact the subject for the purpose of obtaining consent for additional safety evaluations, and subsequent disease-related treatments, if needed. The physician may also recontact the subject for the purpose of obtaining consent to collect information about his or her survival status.

The subject or legally acceptable representative will be given sufficient time to read the ICF and the opportunity to ask questions. After this explanation and before entry into the study, consent should be appropriately recorded by means of either the subject's or his or her legally acceptable representative's personally dated signature. After having obtained the consent, a copy of the ICF must be given to the subject.

After informed consent for the study is appropriately obtained, the subject or his or her legally acceptable representative will be asked to sign and personally date a separate ICF indicating agreement to participate in the optional research component. Refusal to participate in the optional research will not result in ineligibility for the study. A copy of this signed ICF will be given to the subject.

If the subject or legally acceptable representative is unable to read or write, an impartial witness should be present for the entire informed consent process (which includes reading and explaining all written information) and should personally date and sign the ICF after the oral consent of the subject or legally acceptable representative is obtained.

16.2.4. Privacy of Personal Data

The collection and processing of personal data from subjects enrolled in this study will be limited to those data that are necessary to fulfill the objectives of the study.

These data must be collected and processed with adequate precautions to ensure confidentiality and compliance with applicable data privacy protection laws and regulations. Appropriate technical and organizational measures to protect the personal data against unauthorized disclosures or access, accidental or unlawful destruction, or accidental loss or alteration must be put in place. Sponsor personnel whose responsibilities require access to personal data agree to keep the identity of subjects confidential.

The informed consent obtained from the subject (or his or her legally acceptable representative) includes explicit consent for the processing of personal data and for the investigator/institution to allow direct access to his or her original medical records (source data/documents) for study-related monitoring, audit, IEC/IRB review, and regulatory inspection. This consent also addresses the transfer of the data to other entities and to other countries.

The subject has the right to request through the investigator access to his or her personal data and the right to request rectification of any data that are not correct or complete. Reasonable steps will be taken to respond to such a request, taking into consideration the nature of the request, the conditions of the study, and the applicable laws and regulations.

Exploratory PD biomarker, PK and immunogenicity research is not conducted under standards appropriate for the return of data to subjects. In addition, the sponsor cannot make decisions as to the significance of any findings resulting from exploratory research. Therefore, exploratory research data will not be returned to subjects or investigators, unless required by law or local regulations. Privacy and confidentiality of data generated in the future on stored samples will be protected by the same standards applicable to all other clinical data.

16.2.5. Long-Term Retention of Samples for Additional Future Research

Samples collected in this study may be stored for up to 15 years (or according to local regulations) for additional research. Samples will only be used to understand erdafitinib, cetrelimab and co-medications in the protocol, and if applicable, to understand cancer, to understand differential drug responders, and to develop tests/assays related to erdafitinib, cetrelimab and co-medications in the protocol, if applicable. The research may begin at any time during the study or the post-study storage period.

Stored samples will be coded throughout the sample storage and analysis process and will not be labeled with personal identifiers. Subjects may withdraw their consent for their samples to be stored for research (refer to Section 10.3, Withdrawal From the Use of Research Samples).

16.2.6. Country Selection

This study will only be conducted in those countries where the intent is to launch or otherwise help ensure access to the developed product if the need for the product persists, unless explicitly

addressed as a specific ethical consideration in Section 16.1, Study-Specific Design Considerations.

17. ADMINISTRATIVE REQUIREMENTS

17.1. Protocol Amendments

Neither the investigator nor the sponsor will modify this protocol without a formal amendment by the sponsor. All protocol amendments must be issued by the sponsor, and signed and dated by the investigator. Protocol amendments must not be implemented without prior IEC/IRB approval, or when the relevant competent authority has raised any grounds for non-acceptance, except when necessary to eliminate immediate hazards to the subjects, in which case the amendment must be promptly submitted to the IEC/IRB and relevant competent authority. Documentation of amendment approval by the investigator and IEC/IRB must be provided to the sponsor. When the change(s) involves only logistic or administrative aspects of the study, the IEC/IRB (where required) only needs to be notified.

During the course of the study, in situations where a departure from the protocol is unavoidable, the investigator or other physician in attendance will contact the appropriate sponsor representative listed in the Contact Information page(s), which will be provided as a separate document. Except in emergency situations, this contact should be made before implementing any departure from the protocol. In all cases, contact with the sponsor must be made as soon as possible to discuss the situation and agree on an appropriate course of action. The data recorded in the eCRF and source documents will reflect any departure from the protocol, and the source documents will describe this departure and the circumstances requiring it.

17.2. Regulatory Documentation

17.2.1. Regulatory Approval/Notification

This protocol and any amendment(s) must be submitted to the appropriate regulatory authorities in each respective country, if applicable. A study may not be initiated until all local regulatory requirements are met.

17.2.2. Required Prestudy Documentation

The following documents must be provided to the sponsor before shipment of study drug to the study-site:

- Protocol and amendment(s), if any, signed and dated by the principal investigator
- A copy of the dated and signed (or sealed, where appropriate per local regulations), written IEC/IRB approval of the protocol, amendments, ICF, any recruiting materials, and if applicable, subject compensation programs. This approval must clearly identify the specific protocol by title and number and must be signed (or sealed, where appropriate per local regulations) by the chairman or authorized designee
- Name and address of the IEC/IRB, including a current list of the IEC/IRB members and their function, with a statement that it is organized and operates according to GCP and the

applicable laws and regulations. If accompanied by a letter of explanation, or equivalent, from the IEC/IRB, a general statement may be substituted for this list. If an investigator or a member of the study-site personnel is a member of the IEC/IRB, documentation must be obtained to state that this person did not participate in the deliberations or in the vote/opinion of the study

- Regulatory authority approval or notification, if applicable
- Signed and dated statement of investigator (eg, Form FDA 1572), if applicable
- Documentation of investigator qualifications (eg, curriculum vitae)
- Completed investigator financial disclosure form from the principal investigator, where required
- Signed and dated clinical trial agreement, which includes the financial agreement
- Any other documentation required by local regulations

The following documents must be provided to the sponsor before enrollment of the first subject:

- Completed investigator financial disclosure forms from all subinvestigators
- Documentation of subinvestigator qualifications (eg, curriculum vitae)
- Name and address of any local laboratory conducting tests for the study, and a dated copy of current laboratory normal ranges for these tests, if applicable
- Local laboratory documentation demonstrating competence and test reliability (eg, accreditation/license), if applicable.

17.3. Subject Identification, Enrollment, and Screening Logs

The investigator agrees to complete a subject identification and enrollment log to permit easy identification of each subject during and after the study. This document will be reviewed by the sponsor study-site contact for completeness.

The subject identification and enrollment log will be treated as confidential and will be filed by the investigator in the study file. To ensure subject confidentiality, no copy will be made. All reports and communications relating to the study will identify subjects by subject identification and date of birth. In cases where the subject is not randomized into the study, the date seen and date of birth will be used.

The investigator must also complete a subject screening log, which reports on all subjects who were seen to determine eligibility for inclusion in the study.

17.4. Source Documentation

At a minimum, source documents consistent in the type and level of detail with that commonly recorded at the study-site as a basis for standard medical care must be available for the following: subject identification, eligibility, and study identification; study discussion and date of signed ICF;

dates of visits; results of safety and efficacy parameters as required by the protocol; record of all AEs and follow-up of AEs; concomitant medication; drug receipt/dispensing/return records; study drug administration information; and date of study completion and reason for early discontinuation of study drug or withdrawal from the study, if applicable.

The author of an entry in the source documents should be identifiable.

Specific details required as source data for the study and source data collection methods will be reviewed with the investigator before the study and will be described in the monitoring guidelines (or other equivalent document).

The following data will be recorded directly into the eCRF and will be considered source data:

- Race
- Blood pressure and pulse/heart rate
- Height and weight
- Details of physical examination
- The minimum source documentation requirements for Section 4.1, Inclusion Criteria and Section 4.2, Exclusion Criteria that specify a need for documented medical history are as follows:
 - Referral letter from treating physician or
 - Complete history of medical notes at the site
 - Discharge summaries.

Inclusion and exclusion criteria not requiring documented medical history must be verified at a minimum by subject interview or other protocol required assessment (eg, physical examination, laboratory assessment) and documented in the source documents.

An electronic source system may be utilized, which contains data traditionally maintained in a hospital or clinic record to document medical care (eg, electronic source documents) as well as the clinical study-specific data fields as determined by the protocol. This data is electronically extracted for use by the sponsor. If an electronic source is utilized, references made to the eCRF in the protocol include the electronic source system but information collected through electronic source may not be limited to that found in the eCRF. Data in this system may be considered source documentation.

17.5. Case Report Form Completion

Case report forms are prepared and provided by the sponsor for each subject in electronic format. All eCRF entries, corrections, and alterations must be made by the investigator or authorized study-site personnel. The investigator must verify that all data entries in the eCRF are accurate and correct.

The study data will be transcribed by study-site personnel from the source documents onto an eCRF, if applicable. Study-specific data will be transmitted in a secure manner to the sponsor.

Worksheets may be used for the capture of some data to facilitate completion of the eCRF. Any such worksheets will become part of the subject's source documents. Data must be entered into eCRF in English. The eCRF must be completed as soon as possible after a subject visit and the forms should be available for review at the next scheduled monitoring visit.

If necessary, queries will be generated in the eDC tool. If corrections to a eCRF are needed after the initial entry into the eCRF, this can be done in either of the following ways:

- Investigator and study-site personnel can make corrections in the eDC tool at their own initiative or as a response to an auto query (generated by the eDC tool).
- Sponsor or sponsor delegate can generate a query for resolution by the investigator and study-site personnel.

17.6. Data Quality Assurance/Quality Control

Steps to be taken to ensure the accuracy and reliability of data include the selection of qualified investigators and appropriate study sites, review of protocol procedures with the investigator and study-site personnel before the study, and periodic monitoring visits by the sponsor. Written instructions will be provided for collection, handling, storage, and shipment of samples.

Guidelines for eCRF completion will be provided and reviewed with study-site personnel before the start of the study. The sponsor will review the eCRF for accuracy and completeness during on-site monitoring visits and after transmission to the sponsor; any discrepancies will be resolved with the investigator or designee, as appropriate. After upload of the data into the study database they will be verified for accuracy and consistency with the data sources.

17.7. Record Retention

In compliance with the ICH/GCP guidelines, the investigator/institution will maintain all eCRF and all source documents that support the data collected from each subject, as well as all study documents as specified in ICH/GCP Section 8, Essential Documents for the Conduct of a Clinical Trial, and all study documents as specified by the applicable regulatory requirement(s). The investigator/institution will take measures to prevent accidental or premature destruction of these documents.

Essential documents must be retained until at least 2 years after the last approval of a marketing application in an ICH region and until there are no pending or contemplated marketing applications in an ICH region or until at least 2 years have elapsed since the formal discontinuation of clinical development of the investigational product. These documents will be retained for a longer period if required by the applicable regulatory requirements or by an agreement with the sponsor. It is the responsibility of the sponsor to inform the investigator/institution as to when these documents no longer need to be retained.

If the responsible investigator retires, relocates, or for other reasons withdraws from the responsibility of keeping the study records, custody must be transferred to a person who will accept the responsibility. The sponsor must be notified in writing of the name and address of the new custodian. Under no circumstance shall the investigator relocate or dispose of any study documents before having obtained written approval from the sponsor.

If it becomes necessary for the sponsor or the appropriate regulatory authority to review any documentation relating to this study, the investigator/institution must permit access to such reports.

17.8. Monitoring

The sponsor will use a combination of monitoring techniques (central, remote, or on-site monitoring) to monitor this study.

The sponsor will perform on-site monitoring visits as frequently as necessary. The monitor will record dates of the visits in a study-site visit log that will be kept at the study-site. The first post-initiation visit will be made as soon as possible after enrollment has begun. At these visits, the monitor will compare the data entered into the eCRF with the source documents (eg, hospital/clinic/physician's office medical records). The nature and location of all source documents will be identified to ensure that all sources of original data required to complete the eCRF are known to the sponsor and study-site personnel and are accessible for verification by the sponsor study-site contact. If electronic records are maintained at the study-site, the method of verification must be discussed with the study-site personnel.

Direct access to source documents (medical records) must be allowed for the purpose of verifying that the recorded data are consistent with the original source data. Findings from this review will be discussed with the study-site personnel. The sponsor expects that, during monitoring visits, the relevant study-site personnel will be available, the source documents will be accessible, and a suitable environment will be provided for review of study-related documents. The monitor will meet with the investigator on a regular basis during the study to provide feedback on the study conduct.

In addition to on-site monitoring visits, remote contacts can occur. It is expected that during these remote contacts, study-site personnel will be available to provide an update on the progress of the study at the site.

17.9. Study Completion/Termination

17.9.1. Study Completion/End of Study

The end of the study is defined as the last study assessment for the last subject on study or anytime the sponsor terminates the study, whichever comes first.

Prior to Protocol Amendment 5, the final data from the study-site was to be sent to the sponsor (or designee) after completion of the final subject visit at that study-site, in the time frame specified in the clinical trial agreement.

Following Amendment 5, the end of study data collection is defined as when the primary efficacy analysis clinical cutoff has been achieved. At that time, follow up of subjects will end and the eCRF will be closed. Subjects who are continuing to derive benefit from erdafitinib and/or cetrelimab treatment as assessed by their investigator may continue to receive erdafitinib and/or cetrelimab; during this period, only serious adverse events will be monitored and entered into the Company safety repository.

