Subjects who have not received prior systemic therapy for metastatic disease will be stratified by the Eastern Cooperative Oncology Group (ECOG) PS (0-1 versus 2) and assigned randomly (1:1 ratio) to either the erdafitinib monotherapy treatment at the starting oral dose of 8 mg (Arm A), or the combination treatment of erdafitinib and cetrelimab (Arm B). To further characterize safety and clinical activity of the erdafitinib and cetrelimab (Arm B) combination, the dose of erdafitinib and cetrelimab will be administered at 8 mg (no up-titration) and 240 mg Q2W, respectively for Cycles 1 through 4. At Cycle 5, the dosing regimen of cetrelimab is changed from 240 mg Q2W to 480 mg Q4W. Subjects in the Phase 2 dose expansion cohort of the study are cisplatin-ineligible. Cisplatin-ineligible subjects are defined as meeting at least one of the following criteria:

- Impaired renal function defined as calculated by Cockcroft-Gault ([See Attachment 8](#)) ([Galsky 2011](#)).
- Grade 2 or higher peripheral neuropathy per National Cancer Institute Common Terminology Criteria for Adverse Events (NCI-CTCAE version 5.0.)

- Grade 2 or higher hearing loss per NCI-CTCAE version 5.0.
- ECOG Performance Status 2.

On 12 May 2020, the DRC recommended to remove the requirement for up-titration of erdafitinib (to 9 mg daily [QD] dose) from Arm B of Phase 2 erdafitinib + cetrelimab combination based upon emerging safety data.

End of Study Data Collection Timepoint for all ongoing subjects in Phase 1b and Phase 2 (Protocol Amendment 5: [APPENDIX 4](#))

Once the end of study data collection timepoint has been achieved, all subjects will transfer to a streamlined visit schedule to allow for more flexibility with study assessments and to continue to collect required safety information.

SUBJECT POPULATION

Approximately 160 subjects will be enrolled in this study. Thirty subjects are planned to be enrolled in the Phase 1b erdafitinib + cetrelimab cohort. Forty subjects are planned to be enrolled in the Phase 1b erdafitinib + cetrelimab + platinum chemotherapy cohort. Ninety subjects are planned to be enrolled in the Phase 2 erdafitinib +/- cetrelimab cohort.

Phase 1b (Dose Escalation):

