11.4. Efficacy Analyses (Phase 2 Only)

The primary efficacy analysis is planned with ~6 months of follow-up from last patient enrolled or sooner (if last patient discontinued prior to the 6-month follow-up). This will be the final analysis for the study. The primary efficacy analysis will be based on the response assessed by investigators. After the end of study data collection timepoint has been achieved, no further efficacy data will be collected on the eCRF.

To explore the clinical activity of erdafitinib or erdafitinib in combination with cetrelimab in Phase 2, the following efficacy analyses will be performed by each arm in the treated population according to the RECIST 1.1 criteria:

- Primary endpoint: ORR will be estimated with a 95% confidence interval. The primary efficacy analysis will be based on the response assessed by investigators.
- Secondary endpoints: TTR will be summarized descriptively based on responders. The Kaplan-Meier method will be used to estimate the distribution of DoR based on responders. The distributions of PFS and OS will be summarized using similar Kaplan-Meier estimates.

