12.3. Procedures

12.3.1. All Adverse Events

All AEs and special reporting situations, whether serious or non-serious, will be reported starting from the time a signed and dated Full-Study ICF is obtained until 30 days after the last dose of erdafitinib, and 100 days after the last dose of cetrelimab (whichever is longer). If the subject starts a subsequent systemic anticancer therapy, AE data collection will be limited to only Grade ≥ 2 immune-related AEs (for subjects who received cetrelimab) and all SAEs from the date the new anticancer therapy is initiated until 30 days after the last dose of erdafitinib or 100 days after the last dose of cetrelimab, whichever is longer (see table below). Grade 3 and higher AEs, if considered related to study drug, occurring more than 100 days after the last dose of study drug should also be reported. Resolution information after 100 days should be provided. Subjects who discontinue study drug due to drug-related toxicity will continue to be monitored for this toxicity until the toxicity resolves to baseline, stabilizes, or is deemed irreversible, the subject dies, or

subsequent therapy is started, whichever occurs first. Anticipated events will be recorded and reported as described in [Attachment 7](#).

Following Amendment 5, once the end of study data collection timepoint has been achieved, all subjects will transition to the schedule of activities in [APPENDIX 4](#). No further data will be collected on the eCRF. Subjects who are continuing to derive benefit from study treatment as assessed by their investigator may continue to receive study treatment(s); during this period, only serious adverse events will be monitored and entered into the Company safety repository.

Study Treatment	Timing of AE collection
Erdafitinib	All AEs collected until 30 days after the last dose; after this time period, Grade 3 and higher AEs related to study treatment*
Cetrelimab	All AEs collected until 100 days after the last dose; after this time period, Grade 3 and higher AEs related to study treatment*
Following subsequent systemic anticancer therapy	
Erdafitinib	All SAEs collected until 30 days after the last dose
Cetrelimab	Grade ≥ 2 immune-related AEs and all SAEs collected until 100 days after the last dose*

*After the end of study data collection date has occurred, only SAEs will be collected and entered into the Company safety repository.

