3.3.1. Definition of Dose-Limiting Toxicity for Phase 1b (Dose Escalation)

Toxicities will be graded for severity according to the NCI-CTCAE, version 5.0. Only toxicities that occur during the DLT evaluation period will be used to define DLTs and for dose escalation decisions, but toxicities that occur during the entire treatment period will be recorded and considered in decisions regarding the RP2D.

The DLT evaluation period for the Phase 1b erdafitinib + cetrelimab + platinum (cisplatin or carboplatin) chemotherapy cohort is defined as 2 full cycles (6 weeks) of erdafitinib, cetrelimab, and platinum chemotherapy from the start of the first erdafitinib dose.

If the subject receives more than 75% of any of the study drugs in the DLT evaluation period, the subject will be evaluable for DLT. If the subject received less than 75% of each assigned dose due to reasons other than toxicities (eg, disease progression, missed appointments, non-compliance, subject withdrawal), the subject may be replaced with a new subject. All available safety data from subjects will be taken into consideration by the SET. Dose-limiting toxicities are defined as any of the events listed in [Appendix 2 Table 3](#).

Appendix 2 Table 3: Dose-Limiting Toxicity Criteria for Phase 1b: Erdafitinib + Cetrelimab + Platinum Chemotherapy cohort

Criteria for Non-hematological Toxicity	
	Exceptions
• Any Grade 3	Asthenia, anorexia, fever, or constipation
	Fatigue that improves to Grade ≤ 2 in ≤ 7 days
	Nausea lasting for ≤ 7 days responding to BSC ^a
	Vomiting and diarrhea that resolves in ≤ 3 days with BSC ^a
	Laboratory abnormalities that do not require hospitalization and are not felt to be clinically significant by the investigator
	Tumor flare (defined as local pain, irritation, or rash localized at sites of known or suspected tumor) that improves to Grade ≤ 2 in ≤ 7 days
	Elevation in AST or ALT for <7 days
• Any Grade 4	None
• Any Grade 5	None
• Elevation in AST or ALT >3 x ULN meeting criteria for Hy's law ^b	
Criteria for Hematological Toxicity	
Neutrophil count decreased: Grade 4 for >7 days	
Febrile neutropenia: Grade ≥ 3 or 4	
Platelet count decreased: Grade 3 with clinically significant bleeding or Grade 4	
Any Grade 5 toxicity	

Abbreviations: ALT=alanine aminotransferase; AST=aspartate aminotransferase; BSC=best supportive care; ULN=upper limit of normal.

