Section 10 Subject Completion/Discontinuation of Study Treatment/Withdrawal From the Study	Page 117

Section 11 Statistical Methods	Page 118
Section 12 Adverse Event Reporting	Page 123
Section 13 Product Quality Complaint Handling	Page 130
Section 14 Study Drug Information	Page 130
Section 15 Study-Specific Materials	Page 133
Section 16 Ethical Aspects	Page 133
Section 17 Administration Requirements	Page 138

APPENDIX 4: SUGGESTED SCHEDULE OF ACTIVITIES FOR PHASE 1B AND PHASE 2 COHORTS FOLLOWING AMENDMENT 5

Appendix 4 Table 1: Schedule of Activities After End of Data Collection Timepoint (Protocol Amendment 5)
– Phase 1b dose escalation, chemotherapy, and Phase 2 cohorts^{a,b},

Assessments/ Procedure	Notes	Cycle Xc	End-of- Treatment d, e,h
		Day 1 (±2)	Within 30 Days (+7) of last dose
Study Drug Administration			
Erdafitinib	See Sections 6.1 and 6.2.	Oral once daily	
Cetrelimab infusion (Arm B only)	See Sections 6.1 and 6.3.	X	
Safety Assessments			
Vital Signs (temperature, blood pressure, pulse/heart rate, respiratory rate)	See Section 6.3.	X	X
Physical Examination (PE)	Disease-directed PE. See Section 9.6.9.	X	X
Ophthalmologic Exam	To be performed by an ophthalmologist. See Section 9.6.7 for exact assessments.	As clinically indicated	
Adverse Events ^{f,g}		Continuous	
Concomitant Medications ^g		Continuous	
Laboratory Assessments (by local laboratory)			
Hematology	See Section 9.6.2; May be obtained up to 7 days prior to Day 1 of each dose.	X	X
Chemistry	May be obtained up to 7 days prior to Day 1 of each cycle; for exact assessments, see Section 9.6.2.	X	X
PO ₄	May be obtained up to 7 days prior to Day 1 of each cycle; see Section 9.6.2.	X	X
TSH, T3, FT4	May be obtained up to 7 days prior to Day 1 of each cycle; see Section 9.6.2. T3 at Screening then only as clinically indicated.	X (subjects receiving cetrelimab)	X
PTH	Every 3 rd cycle. May be obtained up to 7 days prior to Day 1 of each cycle; Results not required before dosing.	X (subjects receiving cetrelimab)	X
Pregnancy test (pre-dose)	Serum or urine, for women of childbearing potential. See Section 9.6.4.	X	X
Cetrelimab Immunogenicity	An ad-hoc sample for cetrelimab immunogenicity may be collected for purposes of safety evaluation if clinically indicated.		

Assessments/ Procedure	Notes	Cycle Xc	End-of- Treatment d, e,h
		Day 1 (±2)	Within 30 Days (+7) of last dose
Efficacy Assessments			

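### Data collection stops for every cohort at the primary efficacy cutoff, without waiting for the platinum cohort's 6-week DLT windows to finish

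*Protocol*

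**What the plan says.** - **Trigger.** Section 17.9.1 states that after Amendment 5 "the end of study data collection is defined as when the primary efficacy analysis clinical cutoff has been achieved". It continues: "At that time, follow up of subjects will end and the eCRF will be closed". From then on only serious adverse events are monitored, through the company safety repository. Section 12.3.1 repeats this: "No further data will be collected on the eCRF".
- **Timing of the trigger.** Section 11.4, whose heading limits it to Phase 2, says: "The primary efficacy analysis is planned with ~6 months of follow-up from last patient enrolled or sooner". The early case is the last patient discontinuing before 6 months. The phase of that last patient is not stated.
- **Reach.** The Synopsis introduces the rule as "End of Study Data Collection Timepoint for all ongoing subjects in Phase 1b and Phase 2". The title of Appendix 4 Table 1 names the chemotherapy cohort, and a footnote gives that cohort's 3-week cycle.
- **Platinum cohort endpoint.** Appendix 2 Section 2.1 makes the frequency and type of DLT the primary endpoint. Under Appendix 2 Section 3.3.1 the DLT evaluation period "is defined as 2 full cycles (6 weeks) of erdafitinib, cetrelimab, and platinum chemotherapy".
- **Reduced schedule.** Appendix 4 Table 1 has laboratory tests on Day 1 of a cycle and at end of treatment only. It has no platinum row, and its infusion row reads "Cetrelimab infusion (Arm B only".

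**The concern.** An efficacy milestone from one part of the study switches off data capture in another part that has a different primary endpoint. Nothing in 17.9.1, 10.1, 12.3.1 or Appendix 4 makes closure wait until platinum subjects have completed their DLT window, or exempts those still in it.

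What is at stake is the set of DLTs that are not serious adverse events. Two examples from Appendix 2 Table 3 are Grade 4 neutropenia lasting more than 7 days and those Grade 3 non-hematological events that meet no seriousness criterion. After the cutoff these have no route into the data. The dosing data that decide whether a subject is DLT-evaluable (the 75% rule in Appendix 2 Section 3.3.1) also stop.

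Detection suffers as well as recording. Appendix 2 Table 1 schedules hematology and chemistry on Days 1, 8 and 15 of Cycles 1 and 2. With Day 1 tests only, scheduled sampling could not establish that a neutropenia lasted more than 7 days.

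**Working it through.** **1. The window.** 2 cycles × 21 days = 42 days, which reproduces the 6 weeks/42 days in the Synopsis. A platinum subject is inside the window at the cutoff only if C1D1 falls less than 42 days before it.

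**2. Who is exposed if the last patient enrolled means the last Phase 2 patient.** Let the cutoff fall m months after that enrolment, with one month = 365.25/12 days. A platinum subject is exposed if C1D1 is later than week (m × 365.25/12 − 42)/7 after that enrolment.

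| Cutoff (months) | Days | Exposed if C1D1 is later than week |
|---|---|---|
| 6 | 183 | 20.1 |
| 5 | 152 | 15.7 |
| 4 | 122 | 11.4 |
| 3 | 91 | 7.0 |
| 2 | 61 | 2.7 |

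The rows below 6 months are assumptions that show what the early-cutoff clause can do. The protocol gives no date.

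**3. Who is exposed if the last patient enrolled is study-wide.** With the full 6 months, every platinum subject has about 183 days, well above 42, and nobody is exposed. Only an early cutoff could leave anyone in the window.

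**4. Scheduled PK.** Appendix 2 Table 2 samples cetrelimab up to C5D1, which is 4 × 21 = 84 days after C1D1 if cycles run on time. Section 9.3 stops cetrelimab PK sampling at the same timepoint. On the Phase 2 reading with a 6-month cutoff, subjects starting later than week (182.6 − 84)/7 = 14.1 would miss part of it. On the study-wide reading with the full 6 months, nobody would.

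**5. Cohort size.** The plan is 2 × (3 + 6 + 10) = 38 platinum subjects, against approximately 40 stated. The protocol does not say how many were enrolled, or when.

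**6. Appendix 4 against the rest of the protocol.**
- The table covers the Phase 1b cohorts, and every Phase 1b regimen includes cetrelimab (Appendix 1 Table 4, Appendix 2 Table 4). The infusion row nevertheless names Arm B alone, which exists only in Phase 2.
- Section 17.9.1 provides for continued erdafitinib and/or cetrelimab, while Appendix 2 Section 6.4 allows up to 4 platinum cycles. A subject transferred in mid-platinum would have no matching row.

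These mismatches do not depend on accrual.

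**The case against.** **The harm may never occur.** Section 11.4 does not tie the last patient to Phase 2, and it calls this the final analysis for the study, so a study-wide reading is open. The stated purpose of Amendment 5 is to move the remaining subjects on treatment to a lighter schedule, which fits a cohort that has already finished. The missing platinum row fits that too. This stands: the documents do not show that any platinum subject will be inside the window. It does not remove the point, because protection of a primary endpoint should not rest on an unstated reading.

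**Appendix 4 still lists adverse events as continuous.** It does, and its footnote limits collection to serious events only after transition and a completed follow-up visit. But 17.9.1 and 12.3.1 close the eCRF and restrict collection to serious events at the timepoint itself, so this is a further inconsistency and not a safeguard.

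**Stronger readings that the documents do not support.**
- A reader might infer that platinum subjects lose their primary-endpoint data outright. eCRF data up to the cutoff remain, and DLTs that are serious are still reported.
- A reader might infer that most DLT criteria fall outside the serious category. Grade 5 events, febrile neutropenia, Hy's law cases and Grade 3 platelet decreases with significant bleeding would often be serious, and Grade 3 or higher corneal or retinal events must be reported as such (Section 6.2.3.6). The gap is a subset.
- A reader might infer that a missed DLT silently changes an escalation decision, for instance 2/6 (stay) becoming 1/6 (escalate) in Attachment 1. Those table entries are right, but six subjects are planned at the escalated dose, the highest level in Appendix 2 Table 4, so escalation leads to no listed dose. Appendix 2 Sections 3.1.1 and 3.3 also have the SET decide after windows are completed or a DLT occurs. A truncated window would more plausibly delay a decision or reduce the evaluable count.

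**Conclusion.** The point holds as a conditional gap of moderate severity. The protocol states a closure rule that can cut off non-serious DLTs in the platinum cohort, and nothing in the document prevents it.

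The size is unknown and may be zero. It is zero if the cohort has completed, or if the last patient enrolled is study-wide and the full 6 months elapse. On the Phase 2 reading with a 6-month cutoff, it is limited to subjects starting later than about 20 weeks after the last Phase 2 enrolment, and earlier starters are exposed if the cutoff comes forward. A must-fix rating would need evidence that platinum accrual is still open near the cutoff, which the protocol does not give.

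The Appendix 4 mismatch on cetrelimab and platinum stands whatever the accrual status.

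**What to change.** 1. In Section 11.4 (and the Synopsis), state which phase the last enrolled patient belongs to.
2. In Section 17.9.1, with matching text in 10.1 and 12.3.1, set eCRF closure and transfer to Appendix 4 for the platinum cohort at the later of two dates: the primary efficacy cutoff, and the date the last platinum subject completes the DLT window and scheduled PK. Keep Appendix 2 Tables 1 and 2 in force for those subjects until then, and align the PK stop in Section 9.3.
3. Reconcile the Appendix 4 cetrelimab row and the absence of a platinum row with that table's Phase 1b scope, Section 17.9.1 and Appendix 2 Section 6.4. Reconcile its adverse event entry and footnote with 17.9.1 and 12.3.1.

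The cost is a few sentences, and the eCRF may stay open some weeks longer for a few Phase 1b subjects. If the platinum cohort has already completed, items 1 and 2 add no data collection and only the Appendix 4 reconciliation has practical effect.
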